10.4 Statistical Analysis

10.4.1 General Considerations

The quantitative variables will be summarized using mean, median, standard deviation (SD), minimum and maximum. The qualitative variables will be summarized using counts and percentages.

All efficacy analyses will be evaluated at a two-sided $\alpha = 0.05$ and two-sided 95% CIs around the difference between treatments (SkQ1 – placebo) as well as two-sided 95% CIs around the point estimates within each treatment group.

All summaries will be presented by treatment group. Summaries will be provided for demographics, baseline medical history, and subject disposition.

Baseline measures are defined as the last measure prior to the initiation of study treatment (Visit 2). [REDACTED]

10.4.2 Unit of Analysis

Safety endpoints will be analyzed for both eyes. For efficacy endpoints collected at the eye level, the unit of analysis will be the “worst eye” [REDACTED]

10.4.3 Missing Data

The primary efficacy analyses will be performed using Markov Chain Monte Carlo multiple imputation to account for missing Day 57 data. [REDACTED]

In order to show that the primary results are robust to various patterns of missing data, sensitivity models will include the following methods of handling missing data for each primary endpoint:

- Using a control-based pattern mixture for multiple imputation
- Using the last observation carried forward (LOCF) method for missing values
- Analyzing observed data only
- Analyzing observed data for the PP and PPCFS populations for ocular discomfort and conjunctival fluorescein staining, respectively.

Imputation will not be applied for any missing data in the key secondary or exploratory efficacy endpoints.

10.4.4 Multiplicity Adjustments

The primary and key secondary efficacy analyses will be tested following a hierarchical testing strategy in order to maintain a study-wide type I error rate of 0.05 while testing the primary and key secondary hypotheses. The testing strategy will proceed as follows:

- 1) Compare the change from baseline in Ocular Discomfort at Visit 5 (Day 57) [REDACTED] between SkQ1 and placebo. If statistically significant at a two-sided $\alpha = 0.05$, proceed to step 2; otherwise no further testing will be performed and all other testing is considered exploratory.
- 2) Compare the change from baseline in conjunctival fluorescein staining (sum of temporal and nasal regions) at Visit 5 (Day 57) [REDACTED] in the worst eye between SkQ1 and placebo. [REDACTED] If statistically significant at a two-sided $\alpha = 0.05$, proceed to step 3; otherwise no further testing will be performed and all other testing is considered exploratory. Compare the change from baseline in Ocular Discomfort at Visit 3 (Day 29) [REDACTED] between SkQ1 and placebo. If statistically significant at a two-sided $\alpha = 0.05$, proceed to step 4; otherwise no further testing will be performed and all other testing is considered exploratory.
- 3) Compare the change from baseline in conjunctival fluorescein staining (sum of temporal and nasal regions) at Visit 4 (Day 43), [REDACTED] between SkQ1 and placebo. [REDACTED] If statistically significant at a two-sided $\alpha = 0.05$, proceed to step 5; otherwise no further testing will be performed and all other testing is considered exploratory.

- 4) Compare the tear film break-up time pre- to post-CAE[®] change at Visit 5 (Day 57) in the worst eye between SkQ1 and placebo. If statistically significant at a two-sided alpha = 0.05, proceed to step 6; otherwise no further testing will be performed and all other testing is considered exploratory.
- 5) Compare the change from baseline in corneal fluorescein staining in the central region at Visit 3 (Day 29) [REDACTED] [REDACTED] between SkQ1 and placebo. All other testing is considered exploratory.

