6.1.2 Key Secondary Efficacy Measures

The key secondary efficacy endpoints will be tested in a hierarchical fixed sequence in the following order:

1. Change from baseline (Visit 2) in Ocular Discomfort at Visit 3 (Day 29) [REDACTED]
2. Change from baseline (Visit 2) in conjunctival fluorescein staining (sum of temporal and nasal regions) at Visit 4 (Day 43) [REDACTED]
3. Tear film break-up time pre- to post- CAE[®] at Visit 5 (Day 57) in the worst eye at baseline;
4. Change from baseline (Visit 2) in corneal fluorescein staining in central region at Visit 3 (Day 29) [REDACTED]

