10.2 Statistical Hypotheses

The following statistical hypotheses will be tested, with H_{01} , H_{02} , H_{03} , H_{04} , H_{05} , H_{06} tested (in that order) comparing SkQ1 ophthalmic solution versus placebo. Each hypothesis test will be conditional upon the prior test(s) rejecting the null hypothesis. The statistical hypotheses are stated in terms of one-sided hypotheses, although statistical testing will be two-sided. Each test is therefore successful with respect to efficacy if the corresponding null hypothesis is rejected using a two-sided significance level of 0.05.

Primary Efficacy

H_{01} : There is no difference between SkQ1 ophthalmic solution and placebo for the change from baseline in Ocular Discomfort at Visit 5 (Day 57) [REDACTED]

H_{11} : The change from baseline in Ocular Discomfort at Visit 5 (Day 57) [REDACTED] is less with SkQ1 ophthalmic solution than with placebo.

H_{02} : There is no difference between SkQ1 ophthalmic solution and placebo for the change from baseline in conjunctival fluorescein staining (sum of temporal and nasal regions) at Visit 5 (Day 57) [REDACTED]

H_{12} : The change from baseline in conjunctival fluorescein staining (sum of temporal and nasal regions) at Visit 5 (Day 57) [REDACTED] is less with SkQ1 ophthalmic solution than with placebo [REDACTED]

Key Secondary Efficacy

H_{03} : There is no difference between SkQ1 ophthalmic solution and placebo for the change from baseline in Ocular Discomfort at Visit 3 (Day 29) [REDACTED]

H_{13} : The change from baseline in Ocular Discomfort at Visit 3 (Day 29), [REDACTED] is less with SkQ1 ophthalmic solution than with placebo.

H_{04} : There is no difference between SkQ1 ophthalmic solution and placebo for the change from baseline in conjunctival fluorescein staining (sum of temporal and nasal regions) at Visit 4 (Day 43), [REDACTED]

H₁₄: The change from baseline in conjunctival fluorescein staining (sum of temporal and nasal regions) at Visit 4 (Day 43), [REDACTED] is less with SkQ1 ophthalmic solution than with placebo [REDACTED]

H₀₅: There is no difference between SkQ1 ophthalmic solution and placebo for the pre- to post-CAE[®] change in tear film break-up time at Visit 5 (Day 57) in the worst eye.

H₁₅: The pre- to post-CAE[®] change in tear film break-up time at Visit 5 (Day 57) in the worst eye is greater with SkQ1 ophthalmic solution than with placebo.

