10.4.6 Key Secondary Efficacy Variables

The key secondary efficacy endpoint of conjunctival fluorescein staining at Visit 4 (Day 43) will be tested in the ITTCFS population; other key secondary efficacy endpoints will be tested in the full ITT population.

Imputation will not be applied for any missing data in the key secondary efficacy endpoints.

Analyses will use ANCOVA models with baseline values included as covariates. Two-sample t-tests, and Wilcoxon rank sum tests will be performed as sensitivity analyses.

Sensitivity analyses of the conjunctival fluorescein staining endpoint will be performed using the PPCFS population with observed data only. Sensitivity analyses of the other key secondary endpoints will be performed using the PP population with observed data only.

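### Does the misnumbered step list in section 10.4.4 change which key secondary endpoints are tested?

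*Combined protocol and SAP*

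**What the plan says.** Section 10.4.4 lists the comparisons of the hierarchical strategy and, after each of the first five, says which step comes next and that confirmatory testing ends if the result is not significant. Item 2 covers conjunctival staining at Day 57 (H02) and ends with "proceed to step 3; otherwise no further testing will be performed and all other testing is considered exploratory". The same item then runs on, unnumbered, into Ocular Discomfort at Day 29 (H03): "all other testing is considered exploratory. Compare the change from baseline in Ocular Discomfort at Visit 3 (Day 29". H03 carries its own pointer, to step 4. Item 3 is conjunctival staining at Day 43 (H04), with "proceed to step 5; otherwise no further testing will be performed". Item 4 is tear film break-up time at Day 57 (H05), with "proceed to step 6; otherwise no further testing will be performed". Item 5, the last, is central corneal staining at Day 29 (H06).

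Section 10.2 names H01 to H06 and says they are "tested (in that order) comparing SkQ1 ophthalmic solution versus placebo". It adds: "Each hypothesis test will be conditional upon the prior test(s) rejecting the null hypothesis". Section 6.1.2 lists the four key secondary endpoints, Ocular Discomfort at Day 29 first, under the statement "The key secondary efficacy endpoints will be tested in a hierarchical fixed sequence in the following order". Section 6.1.3 states the same gate in general terms: an endpoint is judged only if the tests before it were significant.

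**The concern.** Section 10.4.4 is where a reader looks to see, step by step, which key secondary results count as confirmatory. Its pointers assume six numbered steps and its list has five. A reader who goes by printed number, and takes the first pointer in each item, goes from H02 to H04 and then to H06. Ocular Discomfort at Day 29 and tear film break-up time would drop out of the confirmatory sequence, and Day 43 staining would be tested without the gate that section 10.2 places before it. Item 2 also holds two different pointers (to steps 3 and 4). If both were followed as separate branches, each at 0.05, the study-wide error rate could exceed the stated level. No sentence says which section governs if they differ.

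Section 10.4.6 might seem to add a further contradiction, since it says that "other key secondary efficacy endpoints will be tested in the full ITT population".

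**Working it through.** **Inputs.** Two-sided 0.05 per test (section 10.2); study-wide type I error 0.05 over the primary and key secondary hypotheses (section 10.4.4); the printed item numbers and pointers (section 10.4.4); the order H01 to H06 (section 10.2).

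**Step 1: the plan's own figure.** In a fixed sequence that stops at the first failure, a false rejection can occur only if the first true null reached is rejected. That test is done at 0.05, so the family-wise error is at most 0.05. This reproduces the stated 0.05. Simulation over all 2^6 − 1 = 63 configurations with at least one true null, with false nulls always rejected, gave a worst case of 0.050 at correlations of 0 and 0.5.

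**Step 2: the pointers by printed number.**

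| Comparison | Pointer | Printed item there | Next hypothesis in 10.2 |
|---|---|---|---|
| H01 | step 2 | H02 | H02 |
| H02 | step 3 | H04 | H03 |
| H03 (inside item 2) | step 4 | H05 | H04 |
| H04 | step 5 | H06 | H05 |
| H05 | step 6 | none | H06 |

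One of five is right, three land one hypothesis too far, and one has no target. Taking the first pointer in each item gives H01, H02, H04, H06.

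**Step 3: the same pointers by position.** Count the comparisons in the order in which they are printed: H01 = 1, H02 = 2, H03 = 3, H04 = 4, H05 = 5, H06 = 6. The pointers 2, 3, 4, 5 and 6 then lead to H02, H03, H04, H05 and H06: five of five correct, and all six hypotheses are reached. So the item labels are wrong, and the pointers and the order are right.

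**Step 4: error rate under the misreadings.**

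- First-pointer path (H01, H02, H04, H06): still a fixed sequence, so at most 0.05.
- Both item 2 pointers as parallel branches (H03 then H05; H04 then H06), with one true null in each branch and independent tests: 1 − (1 − 0.05)² = 0.0975. Simulation at correlation 0.5 gave 0.091, and the upper bound is 0.05 + 0.05 = 0.10. To get there, an analyst would have to go on testing in one branch after a failure in the other. The stop clause attached to each of H01 to H05 forbids that, as does section 10.2. With the stop clauses kept, the bound returns to 0.05.

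**Step 5: section 10.4.6.** The sentence assigns analysis populations: the staining subgroup for Day 43 staining and the full ITT population for the rest. It operates under the gate and does not promise that every endpoint is reached, so it neither supports nor contradicts a path.

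**Step 6: source of the slip.** The text was read from PDF, so an extraction fault cannot be ruled out. A simple lost 3) would, however, leave the later items as 4) to 6), and they read 3) to 5). Two items merged in the source list, with automatic renumbering, is the likelier cause.

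**The case for a change.** The best case for a correction is that section 10.4.4 is the operational statement of the gate, that its printed numbers do conflict with section 10.2, and that renumbering costs almost nothing. Made before unmasking, it could not be suspected of following the results. Treating H03 as part of step 2 does not cure the list either, because item 2 then holds two pointers.

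The facts in this stand: the count is six under five, and step 6 is missing. The consequence does not. For two endpoints to be lost, an analyst must follow the first pointer in each item, pass over a full instruction to compare Ocular Discomfort at Day 29 that is printed in the item being carried out, and set aside the explicit order in sections 10.2 and 6.1.2. On arriving at the missing step 6, a reader would see at once that a number had been dropped. A precedence sentence would add nothing, since section 10.2 already fixes the order and the condition. Restoring the number is reasonable housekeeping if the document is reissued for another reason, but it is not needed to run the analysis correctly.

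**Conclusion.** The list in section 10.4.4 contains a numbering slip, and no change to the plan follows. Three places give the same sequence: the hypotheses in section 10.2, the key secondary order in section 6.1.2, and the printed order of comparisons in section 10.4.4. Under it, all six hypotheses are reachable and the study-wide error is 0.05, as stated. The two primary tests are the same on every reading. The omission of two of the four key secondary endpoints, and the 0.0975, arise only on readings that section 10.2 rules out. Renumbering would change no test, error rate, sample size or conclusion.

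This rests on one assumption: that the analyst reads section 10.4.4 together with section 10.2, which defines the hypotheses that the list refers to.

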10.4.5 Primary Efficacy Analyses

Primary efficacy endpoints are:

- Change from baseline (Visit 2) in Ocular Discomfort in the study worst eye at Visit 5 (Day 57) [REDACTED]
- Change from baseline (Visit 2) in conjunctival fluorescein staining (sum of temporal and nasal regions) in the study worst eye at Visit 5 (Day 57) [REDACTED]

[REDACTED]

The primary efficacy endpoints will be analyzed using an analysis of covariance (ANCOVA) model, [REDACTED]. The adjusted least squares means and their standard errors (SEs) will be presented along with their two-sided 95% confidence intervals (CIs) for each treatment group and the difference between the active treatment group and the placebo treatment group. In addition, a two-sample t-test will be used to compare the active and placebo groups in the change from baseline at Visit 5 [REDACTED]. The mean difference, SD for the difference, and the 95% CI for the difference will be presented. A two-sided p-value < 0.05 will be considered statistically significant.

The primary analyses for both primary endpoints will be conducted on the ITT and ITTCFS populations for Ocular Discomfort and conjunctival fluorescein staining, respectively, using the Markov Chain Monte Carlo (MCMC) multiple imputation method to impute missing data. [REDACTED]

[REDACTED] Sensitivity analyses for the ocular discomfort endpoint will also be performed using Last Observation Carried Forward (LOCF) method on the ITT population as well as with the observed data only for both the ITT and PP populations. Sensitivity analyses for the conjunctival fluorescein staining endpoint will be

performed using LOCF on the ITTCFS population as well as with the observed data only for both the ITTCFS and PPCFS populations. Sensitivity analyses using LOCF and observed data only will include Wilcoxon rank sum tests.

10.4.6 Key Secondary Efficacy Variables

The key secondary efficacy endpoint of conjunctival fluorescein staining at Visit 4 (Day 43) will be tested in the ITTCFS population; other key secondary efficacy endpoints will be tested in the full ITT population.

Imputation will not be applied for any missing data in the key secondary efficacy endpoints.

Analyses will use ANCOVA models with baseline values included as covariates. Two-sample t-tests, and Wilcoxon rank sum tests will be performed as sensitivity analyses.

Sensitivity analyses of the conjunctival fluorescein staining endpoint will be performed using the PPCFS population with observed data only. Sensitivity analyses of the other key secondary endpoints will be performed using the PP population with observed data only.

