10 STATISTICAL HYPOTHESES AND METHODS OF ANALYSES

10.1 Analysis Populations

Intent-to-Treat Population – The intent-to-treat (ITT) population includes all randomized subjects. The primary and secondary efficacy analyses will be performed on the ITT population. Subjects in the ITT population will be analyzed as randomized.

Per-Protocol Population – The per protocol (PP) population excludes subjects with significant protocol deviations or who do not complete the study. Protocol deviations will be assessed and the per protocol population identified prior to database lock and unmasking. Subjects in the PP population will be analyzed as treated.

Safety Population – The safety population will include all subjects receiving treatment from whom at least one safety measurement is obtained following the first dose of study drug. The safety population will be analyzed for all safety assessments. Subjects in the Safety population will be analyzed as treated.

In addition, the following populations are defined for the primary and key secondary analyses of conjunctival fluorescein staining:

ITTCFS Population – The ITTCFS population includes all subjects in the ITT population with [REDACTED]

PPCFS Population – The PPCFS population includes all subjects in the PP population with [REDACTED]

The statistical analysis of safety data will be performed for the safety population. The primary efficacy analysis of Ocular Discomfort will be performed on the ITT population. The primary efficacy analysis of conjunctival fluorescein staining will be performed on

the ITTCFS population. Key secondary efficacy analyses will be performed on the ITT population, except for analysis of conjunctival fluorescein staining, which will be performed on the ITTCFS population. Exploratory efficacy analyses will be performed on the ITT population. The primary efficacy analysis procedures will also be performed on the PP and PPCFS populations as sensitivity analyses, for Ocular Discomfort and conjunctival fluorescein staining, respectively.

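### Do the alpha-controlled key secondary endpoints need a missing-data sensitivity analysis beyond observed cases?

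*Combined protocol and SAP*

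**What the plan says.** Sections 10.2 and 10.4.4 put two primary and four key secondary hypotheses into one fixed sequence, "in order to maintain a study-wide type I error rate of 0.05 while testing the primary and key secondary hypotheses". The key secondaries are ocular discomfort at Day 29 (H03), conjunctival staining at Day 43 (H04), the pre- to post-CAE "change in tear film break-up time at Visit 5 (Day 57) in the worst eye" (H05), and central corneal staining at Day 29 (H06).

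For these four, Section 10.4.6 says "Imputation will not be applied for any missing data in the key secondary efficacy endpoints". The synopsis and Section 10.4.3 give the same rule. The main analysis is ANCOVA with the baseline value as covariate. H03, H05 and H06 are tested in the ITT population. For H04, "The key secondary efficacy endpoint of conjunctival fluorescein staining at Visit 4 (Day 43) will be tested in the ITTCFS population", and the threshold that defines that population is redacted.

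The supporting analyses are a t-test, a Wilcoxon test and a restricted population: "Sensitivity analyses of the other key secondary endpoints will be performed using the PP population with observed data only", with PPCFS playing that part for H04. Section 10.1 defines the restriction: "The per protocol (PP) population excludes subjects with significant protocol deviations or who do not complete the study".

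The primaries are treated differently. They use MCMC multiple imputation, and in Section 10.4.3 "sensitivity models will include the following methods of handling missing data for each primary endpoint", followed by control-based pattern mixture, LOCF and observed-data analyses.

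**The concern.** Tests that spend the same alpha as the primaries appear to get a weaker safeguard. A single-visit ANCOVA without imputation uses only subjects seen at that visit, even though the population is labelled ITT. The t-test and Wilcoxon test change the test statistic and leave the missing-data assumption alone. The PP analysis narrows the data further: it drops subjects who have a Day 29 or Day 43 value but leave later. The contrast is plainest at Visit 5, where an absent subject is imputed for both primaries and omitted from H05.

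At stake is the credibility of a borderline key secondary claim. If subjects who do badly leave SkQ1 more often than placebo, the observed-case difference is biased towards SkQ1. If they leave placebo more often, it is biased the other way. None of the analyses listed for H03 to H06 tests this directly.

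**Working it through.** **The plan's own figure.** Section 10.3 requires 284 per group for 90% power. The effect and SD are redacted, so 284 cannot be rebuilt from its inputs. Solved backwards, it implies a standardised effect of (1.960 + 1.282) × √(2/284) = 0.272. None of the results below depends on this.

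**Inputs.**
- From the documents: 300 per arm, 1:1 allocation, two-sided 0.05.
- Inferred: if 300 against 284 is a dropout allowance, loss by Day 57 is (300 − 284)/300 = 5.3%. With linear loss (assumption), that is 5.3% × 28/56 = 2.7% by Day 29 and 5.3% × 42/56 = 4.0% by Day 43.
- Assumed: missing rates by arm (m_S for SkQ1, m_P for placebo), and a shift k, the number of residual SDs by which unobserved outcomes are worse than observed ones in the same arm.

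**Formulas, with no true difference over all randomised subjects.**
- Bias towards SkQ1 = k × (m_S − m_P)
- SE = √(1/n_S + 1/n_P), with n = 300 × (1 − m)
- False-positive rate in favour of SkQ1 = 1 − Φ(1.96 − bias/SE), nominally 2.5%
- Tipping shift for p = 0.03, with missing placebo subjects like observed ones = (2.170 − 1.960) × SE / m_S

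| Missing, SkQ1 vs placebo | k | Bias (SD) | SE | Rate in favour of SkQ1 | Tipping shift at p = 0.03 |
|---|---|---|---|---|---|
| 3% vs 2% | 0.5 | 0.005 | 0.0827 | 2.9% | 0.58 SD |
| 4% vs 2% | 0.5 | 0.010 | 0.0829 | 3.3% | 0.44 SD |
| 6% vs 3% | 0.5 | 0.015 | 0.0836 | 3.75% | 0.29 SD |
| 6% vs 3% | 1 | 0.030 | 0.0836 | 5.5% | 0.29 SD |
| 5% vs 5% | 1 | 0 | 0.0838 | 2.5% | not applicable |
| 3% vs 6% | 0.5 | −0.015 | 0.0836 | 1.6% | not applicable |

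The first two rows fit Day 29 (H03, H06), where inferred loss is about 2.7%. The 6% vs 3% rows average 4.5%, which is plausible at Day 57 (H05) but high for Day 29. If missing subjects in both arms are shifted equally, the tipping shift at 6% vs 3% is 0.59 SD.

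For H04 the ITTCFS size is redacted. At an assumed 100, 150 or 200 per arm, 6% vs 3% with k = 1 gives 4.0%, 4.4% or 4.8%.

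**Would extending control-based imputation help?** Write the observed means as −k·m_S for SkQ1 and −k·m_P for placebo (lower is better). Filling missing SkQ1 values from placebo gives

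(1 − m_S)(−k·m_S) + m_S(−k·m_P) − (−k·m_P) = −k(m_S − m_P)(1 − m_S).

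The bias is multiplied by (1 − m_S). At 6% vs 3% with k = 1 it goes from 0.030 to 0.030 × 0.94 = 0.028 SD, which by itself takes the rate from 5.5% to 1 − Φ(1.96 − 0.0282/0.0836) = 5.2%.

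A simulation (6,000 trials per scenario, imputation from the placebo regression on baseline, 10 imputations, Rubin's rules) gave a larger fall, from 5.6% to 4.4%. It also gave a fall from 2.4% to 2.1% at 5% vs 5%, where there is no bias to remove, although that difference is about one Monte Carlo SE. A second run (3,000 trials, 6% vs 3%, k = 1, baseline correlation 0.5 assumed) explains the pattern: Rubin's SE was 0.084 against an empirical SE of 0.078. Most of the fall therefore comes from a conservative variance.

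**What the plan already shows.** Section 10.4.1 requires disposition by treatment group, Section 8.6.2 records reasons for discontinuation, and Section 10.4.8 tabulates adverse events leading to discontinuation by arm. Section 10.4.3 runs control-based imputation and LOCF on ocular discomfort and conjunctival staining at Day 57, the same measures as H03 and H04 at a later visit.

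**The case for a change.** The strongest case for a change is consistency. The plan sets its own standard by asking that the primary results be robust to various missing-data patterns, then does not apply it to claims under the same alpha. Extending the control-based analysis would take about one sentence in Sections 10.4.3 and 10.4.6, and no new data or alpha. Specified before unmasking it would be credible; added after a borderline result it would look post hoc. Section 10.4.6 shows no redaction that could hide such an analysis.

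Much of this stands. The difference in treatment is real, and the plan's indirect evidence is weakest for H05 and H06, whose measures are not primary endpoints. But consistency alone does not change a result. The observed-data ANCOVA would still decide the hierarchy, and the proposed check hardly moves the bias it is meant to expose. For H05 it would also need an imputation model that is hard to write: the visible procedures in Section 8.3.1 list tear film break-up time twice only at Visit 5, so no earlier pre- to post-CAE change is visible to support it (redaction prevents certainty).

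**Conclusion.** The plan can stand. Observed-case ANCOVA is a deliberate choice, stated the same way in three places. It is valid if missingness depends only on treatment and baseline, and outcome-related loss that is similar in both arms does not bias it either. Harm needs three things together: both primaries (and any earlier key secondary) significant, informative dropout that differs between arms, and a borderline result.

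At Day 29 losses consistent with the 284 versus 300 margin, the favourable error rate would be about 2.9% to 3.3% instead of 2.5%. For H05 at Day 57 it would be 3.75% with a 0.5 SD shift, and 5.5% only if lost subjects are a full SD worse and SkQ1 loses twice as many. These figures rest on reading the margin as dropout, on linear loss, and on imbalances and shifts that the documents neither state nor suggest. The rates apply per test, given that the test is reached.

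If the sponsor wants more, a delta-adjusted tipping-point analysis addresses the named risk better than control-based imputation, with the observed-case ANCOVA still deciding the hierarchy. That is an optional refinement and would not alter any planned decision.
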